## 10.1 Analysis sets

### 10.1.1 Full Analysis Set

The Full Analysis Set (FAS) includes all patients who received at least one dose of PDR001. Patients will be analyzed according to the planned treatment (regimen). The FAS will be used for all listings of raw data. Unless otherwise specified, the FAS will be the default analysis set used for all analyses.

### 10.1.2 Safety Set

The Safety Set includes all patients from the FAS who have received at least one dose of PDR001 and had at least one valid post-baseline safety assessment. The statement that a patient had no AEs (on the AE eCRF) constitutes a valid safety assessment. Patients will be classified according to treatment received, where treatment received is defined as:

1. The treatment assigned if it was received at least once, or
2. The first treatment received when starting therapy with study treatment if the assigned treatment was never received.

The safety set will be used for the safety summary of the study.

### 10.1.3 Per-Protocol Set

The Per Protocol Set (PPS) consists of a subset of FAS patients in the phase II part who meet the following criteria:

- Presence of at least one measurable lesion at baseline according to RECIST 1.1 as per [Appendix 1](#).
- At least 2 post-baseline tumor assessments (unless disease progression is observed before that time)
- Have not been previously treated with PD-1- or PD-L1-directed therapy

Patients will be classified according to treatment received.

The PPS will be used in the phase II part of the study only and will define the patients used in the sensitivity analysis of the primary endpoint (see [Section 10.4.4](#)). If the PPS and the FAS are identical, then analyses described by the PPS below will not be performed.

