### **10.4.3 Handling of missing values/censoring/discontinuations**

Patients in the dose escalation part who are ineligible for the DDS will be excluded from the primary analysis, although their data will be used for all remaining analyses.

Patients in the phase II part who have Best Overall Response (BOR) of UNK or NA will be considered as a treatment failure in the primary analysis of ORR. Patients with individual scans of UNK or NA will be handled according to RECIST 1.1 as per [Appendix 1](#).

Other missing data will simply be noted as missing on appropriate tables/listings.

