### **10.4.4 Supportive analyses**

As a supportive analysis of the primary endpoint for Phase II, a Bayesian hierarchical model with a flexible exchangeability design will be applied on ORR including data from all indications. Exchangeability of indication parameters will be assessed; for the Bayesian methodology and an application to binary data see [Thall \(2003\)](#) and [Chugh \(2009\)](#).

Moreover, the primary analysis of the phase II will be repeated using the PPS.

If there is a substantial number of patients receiving palliative radiotherapy, sensitivity analyses of ORR will be performed where the tumor response assessments are censored at the time of palliative radiotherapy. BOR is determined by the best response recorded between the date of first dose of treatment and date of objectively documented progression or date of subsequent anticancer therapy (including on-treatment palliative radiotherapy of non-target or target lesions), whichever occurs first.

Additional supportive [REDACTED] analyses will be conducted to support the primary objective, if appropriate, and the details of these analyses will be defined in the RAP.

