- PR = at least two determinations of PR or better at least 4 weeks apart before progression (and not qualifying for a CR) where confirmation required or one determination of PR prior to progression where confirmation not required
- SD = at least one SD assessment (or better) > 6 weeks after randomization/start of treatment (and not qualifying for CR or PR).
- PD = progression ≤ 12 weeks after randomization/ start of treatment (and not qualifying for CR, PR or SD).
- UNK = all other cases (i.e. not qualifying for confirmed CR or PR and without SD after more than 6 weeks or early progression within the first 12 weeks)

Overall lesion responses of CR must stay the same until progression sets in, with the exception of a UNK status. A patient who had a CR cannot subsequently have a lower status other than a

PD, e.g. PR or SD, as this would imply a progression based on one or more lesions reappearing, in which case the status would become a PD.

Once an overall lesion response of PR is observed (which may have to be a confirmed PR depending on the study) this assignment must stay the same or improve over time until progression sets in, with the exception of an UNK status. However, in studies where confirmation of response is required, if a patient has a single PR ( $\geq 30\%$  reduction of tumor burden compared to baseline) at one assessment, followed by a  $< 30\%$  reduction from baseline at the next assessment (but not  $\geq 20\%$  increase from previous smallest sum), the objective status at that assessment should be SD. Once a confirmed PR was seen, the overall lesion response should be considered PR (or UNK) until progression is documented or the lesions totally disappear in which case a CR assignment is applicable. In studies where confirmation of response is not required after a single PR the overall lesion response should still be considered PR (or UNK) until progression is documented or the lesion totally disappears in which case a CR assignment is applicable.

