### 14.1.3.2 Time to event variables

#### 14.1.3.2.1 Progression-free survival

Usually in all Oncology studies, patients are followed for tumor progression after discontinuation of study medication for reasons other than progression or death. If this is not used, e.g. in Phase I or II studies, this should be clearly stated in the protocol. Note that randomized trials (preferably blinded) are recommended where PFS is to be the primary endpoint.

**Progression-free survival (PFS)** is the time from date of randomization/start of treatment to the date of event defined as the first documented progression or death due to any cause. If a patient has not had an event, progression-free survival is censored at the date of last adequate tumor assessment.

[REDACTED]

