2.2 Imputation rule of partial or missing dates/data

Imputation rule of partial or missing dates

As a general rule, when a date is recorded as a partial date, the missing day is imputed to the 15th of the month (e.g., DEC2007 imputed to 15DEC2007), and if the day and month are both missing then to July 1st of that year (e.g., 2007 imputed to 01JUL2007). Such imputed data are flagged in the listings.

Imputation rules for AEs, medical history and concomitant medications partial or missing dates are defined in Section 4.1.1.

In order to be conservative, these rules tend to maximize the duration of AEs under treatment and are equivalent to the rule above otherwise.

For other partial dates, the general STL standard imputation rules are used.

For computation of time intervals (e.g. elapse time between initial diagnosis to first recurrence/relapse), if the imputation rule leads to a negative value, time interval should be set to missing.

Handling of missing values/censoring/discontinuation

Continuing events (e.g. AEs) will be summarized using the data cut-off date as the date of completion, with an indication within listings that the event is continuing. For patients who discontinue the study with ongoing events, the discontinuation date is used as the completion date of the event with the appropriate censoring.

The reasons for discontinuation from study will be listed, along with dates of first and last study treatment, and date of discontinuation for each patient.

Other missing data will simply be noted as missing on appropriate tables/listings.

2.3 **Analysis sets**

A patient must have given informed consent to participate in the study before being included in any analysis set.

Patients will be excluded from the analysis sets based on the protocol deviations and specific non-protocol deviations entered in the database. All protocol deviations and non-protocol deviations leading to exclusion from specific analysis set will be identified before database lock.

See Table 2-1 for non-protocol deviation leading to exclusion from analysis set definitions, and Table 2-2 for protocol deviation leading to exclusion from analysis set definitions.

All protocol deviations will be listed by treatment.

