2.3.8 Analysis set exclusion

Patients will be excluded from the analysis sets based on the protocol deviations and specific non-protocol deviations entered in the database. All protocol deviations and non-protocol deviations leading to exclusion from specific analysis sets will be identified before database lock. Protocol and non-protocol deviations leading to exclusion from specific analysis sets and reasons for exclusion from populations will be tabulated/listed by treatment (Phase I) /indication and treatment (Phase II).

Table 2-1 displays non-protocol deviations leading to exclusion from analysis set definitions and Table 2-2 displays protocol deviations leading to exclusion from analysis set definitions.

Table 2-1 Non-protocol deviation leading to exclusion from analysis set definitions

Summary of non PD	Analysis set(s) to be excluded
No valid post-baseline safety assessment	SS
No administration of study treatment	FAS, SS, PPS, DDS, DDP, PAS,
	Immunogenicity prevalence set, Immunogenicity incidence set
 Patient, who has not experienced DLT, was not observed for ≥ 28 days following the C1D1 or had not completed the required safety evaluations for Cycle 1 or 	DDS
 Patient who has not experienced DLT, received <70% planned doses at each time of dosing in Cycle 1. 	
The patient did not receive at least one dose of PDR001 during cycle 1 or did not have sufficient PK data in cycle 3 to evaluate the AUC _(0-336h) .	DDP
Patient did not have at least one measurable PDR001 concentration in cycle 1	PAS
No determinant IG sample at both baseline and post-baseline	Immunogenicity prevalence set
No determinant IG sample at baseline or post- baseline or both	Immunogenicity incidence set

Table 2-2 Protocol deviation leading to exclusion from analysis set definitions

Protocol Deviation ID (DVSPID)	Summary of PD	Analysis set(s) to be excluded
INCL01	Written informed consent must be obtained prior to screen procedures.	FAS, SS, PPS, DDS, DDP, PAS, Immunogenicity prevalence set, Immunogenicity incidence set

Novartis	Confidential	Page 22
SAP final CSR	24-Jul-2020 (11:48)	CPDR001X2101

	,	,
Protocol Deviation ID (DVSPID)	Summary of PD	Analysis set(s) to be excluded
INCL04	In the Phase II part, patient does not have at least one tumor lesion meeting measurable disease criteria as determined by RECIST v1.1.	PPS
INCL05	In the Phase II part, patient was not a patient with either NSCLC, melanoma, TNBC, or ATC.	PPS

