3.4 Efficacy evaluation

Analysis of efficacy endpoints will be performed using the FAS.

Assessment by irRC

For irRC (see [CPDR001X2101 Amendment 8 Appendix 14.2]) the key difference from RECIST v1.1 (see [CPDR001X2101 Amendment 8 Appendix 14.1]) in the assessment of these endpoints is the recommendation that irPD be confirmed at least 4 weeks after the criteria for irPD are first met. A single assessment of irPD followed by a subsequent assessment of irSD or better will be considered as a pseudo-progression, these are not considered as progression events for the purposes of analysis. Where irPD is confirmed by a second assessment, the date of the first of these two assessments is then the date of progression. For patients who have ended treatment without a valid confirmation assessment, for the purposes of analysis the single assessment of irPD will be treated as a confirmed irPD. At time of analysis there may be patients whose last adequate assessment is an unconfirmed irRC progression but who are continuing treatment. In these cases that progression will be treated as a confirmed progression for the primary analysis, and sensitivity analysis of time to event endpoints may be conducted in which the patient is censored at the time of last adequate assessment. Additional definitions and derivation rules for irRC are provided in Section 4.2.

Best overall response (BOR)

The BOR is the best response recorded from the start of the treatment until disease progression/recurrence. For RECIST v1.1 and irRC, any assessments taken before the start of any further antineoplastic therapy will be considered in the assessment of BOR in recognition that response to immunotherapy may be delayed. For both RECIST v1.1 and irRC, if any alternative antineoplastic therapy is taken while on study, any subsequent assessments will be excluded from the BOR determination.

Per RECIST v1.1, CR and PR need to be confirmed with at least two determinations of CR or PR respectively at least 4 weeks apart before progression. In order to classify overall response as SD, a patient must have at least one SD assessment (or better) > 6 weeks after start date of study treatment. In order to classify overall response as PD, a patient must have progression < 12 weeks after start date of study treatment.

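### The per-protocol set drops patients who die before a second scan without observed progression, so its scan criterion can only leave the ORR unchanged or raise it; SAP 2.3.3 and SAP Tables 2-1/2-2 also define different per-protocol sets

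*Protocol*

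**What the plan says.** Protocol 10.1.3 builds the PPS from phase II FAS patients who meet three criteria: a measurable lesion at baseline, no earlier PD-1/PD-L1 therapy, and "At least 2 post-baseline tumor assessments (unless disease progression is observed before that time". SAP 2.3.3 repeats all three. Protocol 10.4.4 gives the set its purpose: "Moreover, the primary analysis of the phase II will be repeated using the PPS".

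The FAS (Protocol 10.1.1) keeps everyone who received a dose. Under Protocol 10.4.3 a patient whose best response is unknown or not assessed "will be considered as a treatment failure in the primary analysis of ORR".

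Progression and death are separate events in these documents. Protocol Appendix 1, 14.1.3.2.1 defines the PFS event as "the first documented progression or death due to any cause".

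Response must be confirmed. Appendix 1, 14.1.3.1 states "PR = at least two determinations of PR or better at least 4 weeks apart before progression" where confirmation is required, and requires it for non-randomized trials with response as the primary endpoint. SAP 3.4 agrees: "CR and PR need to be confirmed with at least two determinations of CR or PR respectively at least 4 weeks apart before progression".

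On how exclusions are made, SAP 2.3 says "Patients will be excluded from the analysis sets based on the protocol deviations and specific non-protocol deviations entered in the database" and points to Tables 2-1 and 2-2. SAP 2.3.8 repeats this and adds that "reasons for exclusion from populations will be tabulated/listed by treatment".

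**The concern.** A sensitivity analysis of a response rate should be able to show that the primary result is fragile. The scan criterion cannot do that. It exempts one kind of early failure (observed progression) but not another (death), and nobody it removes can be a responder. Through this criterion the PPS result can only equal or exceed the FAS result. A reader who sees the two agree, or sees the PPS come out higher, learns little about robustness.

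The second issue is which patients are in the PPS at all. The SAP says exclusions follow recorded deviations and lists those deviations in two tables, but the tables do not match the definition a few pages earlier. Two programmers working from the same SAP could build two different sets.

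**Working it through.** **1. Reproduce the plan's figures.** Protocol 10.4.2 uses a Beta(0.25, 1) prior, so with r responders among n patients the posterior is Beta(0.25 + r, 1 + n − r).

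- NSCLC, 12/60: Beta(12.25, 49) gives P(ORR > 15%) = 83.7%, as stated.
- Melanoma, 18/60: Beta(18.25, 43) gives P(ORR > 20%) = 96.2%, as stated.

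**2. Where the patient goes.** Take a patient who dies before a second assessment without observed progression.

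| | FAS | PPS |
|---|---|---|
| Included? | Yes, one dose suffices | No, fewer than two assessments and the exemption does not apply |
| Effect on ORR | In the denominator as a non-responder | None |

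With no scan, the best response is unknown and counts as failure. With one scan that is not progression, it is stable disease at best, even if that scan showed a partial response, because confirmation is missing.

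**3. Direction.** A confirmed response needs two determinations at least 4 weeks apart, so every responder has two post-baseline assessments and passes. If the criterion drops k patients, all are non-responders and the ORR goes from r/n to r/(n − k). This is never lower than r/n, and it is higher whenever r ≥ 1 and k ≥ 1. An exhaustive check for n up to 120 found no exception, for the observed rate or the posterior mean.

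**4. Size.** The documents do not give k. For one patient, 12/60 = 20.00% becomes 12/59 = 20.34%, a shift of 0.34 percentage points.

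The larger fractions below are assumptions chosen only to show scale. They cover everyone dropped by the scan criterion, not deaths alone, and they assume the other two PPS criteria exclude nobody.

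| Dropped (assumed) | NSCLC ORR | P(ORR > 15%) | Melanoma ORR | P(ORR > 20%) |
|---|---|---|---|---|
| 0 of 60 | 12/60 = 20.0% | 83.7% | 18/60 = 30.0% | 96.2% |
| 6 of 60 (10%) | 12/54 = 22.2% | 91.1% | 18/54 = 33.3% | 98.7% |
| 18 of 60 (30%) | 12/42 = 28.6% | 98.5% | 18/42 = 42.9% | 99.9% |

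**5. SAP definition against SAP tables.**

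| PPS rule | SAP 2.3.3 | Tables 2-1/2-2 |
|---|---|---|
| Measurable lesion at baseline | Yes | Yes (INCL04) |
| Two post-baseline assessments | Yes | Not listed |
| No prior PD-1/PD-L1 therapy | Yes | Not listed |
| One of the four tumour types | Not listed | Yes (INCL05) |

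The remaining PPS rows, no study treatment and missing consent (INCL01), remove patients from the FAS as well and cause no conflict.

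**The case against.** **The conservative analysis is already primary.** The FAS counts these patients as failures, and no decision rule is tied to the PPS. This stands, and it keeps the point minor.

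**The one-way property survives the fix.** Patients who stop early for an adverse event, withdraw or are lost before a second scan are also all non-responders. Any minimum-scan rule combined with confirmed response behaves this way. This stands too. The change removes one source of the shift, and the rest needs a sentence beside the result.

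**The plan limits the number dropped.** Protocol 7.2.1 requires an end-of-treatment scan unless one was done in the previous 30 days. Protocol 7.1.6 continues tumour assessment after many types of discontinuation. Observed progression is exempt. All this is correct, and it is a reason not to treat 10% or 30% as expected values.

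**If the tables govern, the scan criterion is never applied.** That is possible. The dataset specifications and the full deviation list (SAP 3.1.6 places the latter in another document) are not available here, so nothing can be said about how the PPS is programmed. The conflict between text and tables remains either way.

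A reader might also infer three stronger things that the documents do not support:

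- *That the whole PPS can only give a higher ORR than the FAS.* The measurable-lesion and prior-therapy criteria could remove responders, and the PPS classifies by treatment received where the FAS uses planned treatment.
- *That the exclusion is large in anaplastic thyroid cancer.* The Amendment 06 rationale says most early patients progressed or died before the first scan. It does not separate the two, observed progression is exempt, and that amendment then changed the entry criteria.
- *That the PPS could turn a missed activity bar into a pass.* The arithmetic allows it: 11/60 = 18.3%, but 11/54 = 20.4% after six exclusions. However, the rule in Protocol 10.4.2 is stated as counts out of 60 under the primary analysis, and no passage applies it to the PPS.

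**Conclusion.** The point holds and is minor. On the literal wording, early death without observed progression removes a patient from the PPS, and this criterion can only leave unchanged or raise the PPS ORR. The direction is certain because response must be confirmed. The size is unknown: 0.34 percentage points for one patient in the NSCLC example, and anything larger rests on an assumed fraction. The documents do not say whether clinical progression counts as observed progression, which also affects how many patients are dropped. The FAS primary analysis and the activity rule are unaffected.

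The mismatch between SAP 2.3.3 and Tables 2-1/2-2 needs no assumption: two criteria are missing from the tables and one is missing from the text.

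**What to change.** - In Protocol 10.1.3 and SAP 2.3.3, change the exemption to *unless disease progression or death occurs before that time*. Count these patients as non-responders, and state whether clinical progression counts as observed progression.
- Align SAP 2.3.3 with Tables 2-1/2-2 in both directions: add rows for the two-assessment and prior PD-1/PD-L1 criteria, and either add INCL05 to 2.3.3 or remove it from the table.
- Report PPS exclusions by reason, which SAP 2.3.8 already plans to tabulate or list. Note beside the result that the remaining exclusions under the scan criterion are also all non-responders, so it still leans upward.

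The cost is one clause in each document, a few table entries and one sentence in the report. The PPS ORR becomes equal or less favourable, and the PPS moves closer to the FAS. Enrolment ended in March 2018, Protocol 8.5 has the primary endpoint monitored quarterly, and the SAP is dated July 2020. If the change is made after data were seen, label it post hoc and show the PPS under both definitions.

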### 10.1.4 Dose-determining safety set

The DDS consists of all patients from the safety set in the phase I dose escalation part who either meet the following minimum exposure criterion and have sufficient safety evaluations, or have experienced a DLT during Cycle 1. A patient is considered to have met the minimum exposure criterion if he/she received at least 70% of the planned dose of PDR001 at each time of dosing during Cycle 1.

Patients who do not experience DLT during the first cycle are considered to have sufficient safety evaluations if they have been observed for  $\geq 28$  days following the first dose, and are considered by both the Sponsor and Investigators to have enough safety data to conclude that a DLT did not occur.

Patients who do not meet these minimum safety evaluation requirements will be regarded as ineligible for the DDS and an additional patient may be recruited (see [Section 7.1.4.1](#)).

#### **10.1.5 Dose-determining pharmacokinetic set**

The dose-determining pharmacokinetic set (DDP) consists of all patients in the Phase I dose escalation part who have received at least one dose of PDR001 during Cycle 1 and have sufficient PK data in cycle 3 to evaluate the  $AUC_{(0-336h)}$ .

#### **10.1.6 Pharmacokinetic analysis set**

The pharmacokinetic analysis set (PAS) consists of all patients who have at least one blood sample providing evaluable PK data. The PAS will be used for summaries of PK concentration data, and PK parameters, except that DDP will be used in the dose-exposure analysis at Phase I.

Note: Patients may be removed from the estimation of certain PK parameters on an individual basis depending on the number of available blood samples. These patients will be identified at the time of analysis.

